7.6 Health Economic Endpoints

Hospitalization data will be analyzed for live subjects in the mITT population.

Unscheduled hospitalizations post index procedure are considered as re-hospitalizations. The number of hospitalized subjects who died during the index procedure or re-hospitalizations will be summarized separately.

Subjects with missing admission or discharge date for whom the calculation of length of stay (LOS) cannot be performed will be excluded from calculation, e.g., withdrawal from study prior to discharge etc. However, they will still be counted towards the number of index procedure hospitalizations and re-hospitalizations, as applicable.

- **Hospitalization length of stay for index procedure**

LOS in hospitalizations due to index procedure will be summarized at the subject level per the following formula.

$$\text{Length of stay (days)} = \text{discharge date} - \text{admission date} + 1.$$

LOS will be summarized for subjects who were discharged alive following index procedure. The overall LOS, and LOS at ICU will be summarized separately. Further, the number and percentage of subjects with hospitalization length of stay will be summarized in categories: 0 to ≤ 1 day, > 1 to ≤ 2 days, and > 2 days.

Discharge location will be summarized for subjects who were discharged alive following study procedure.

- **Unscheduled re-hospitalizations post index procedure**

The number and percentage of subjects with at least one re-hospitalization, the number of re-hospitalizations (including re-hospitalizations without discharge due to reasons such as death or early withdrawal), the maximum length of stay across re-hospitalizations will be summarized for subjects who were discharged alive from index procedure. The maximum length of stay is taken to be the maximum number of stay, in days, across all re-hospitalizations at the subject level.

7.7 Clot Analysis

Subjects with any clot composition data (e.g., red blood cells, fibrin measurements) from at least one pass will be included into the clot analyses. Study passes without clots retrieved will be excluded from analyses. Missing data of clot dimension or composition

from the central clot are anticipated to be very small. Missing data on clot composition or dimension will be excluded from analysis, should there be any.

Composition of clot components to be evaluated includes RBC, WBC, fibrin, collagen, platelets, and Von Willebrand Factor (vWF), as evaluated from the Central Lab, will be summarized per pass, and overall using mITT analysis set. The clot weight (mg) and area (mm²) will also be summarized per pass and overall in same way.

The total area (across all passes with clots extracted and clot composition measured from central lab) will be calculated to sum up the area from all individual pass with clots. The total weight (across all passes) will be calculated in the same fashion as the total area.

The total amount of RBC (across all passes, %) in terms of area (A) =

$$RBC_{pass\ 1}(\%) \times \frac{A_{pass\ 1}}{Total\ A} + RBC_{pass\ 2}(\%) \times \frac{A_{pass\ 2}}{Total\ A} + \dots + RBC_{pass\ n}(\%) \times \frac{A_{pass\ n}}{Total\ A}$$

The total amount of RBC (across all passes, %) in terms of weight (W) =

$$RBC_{pass\ 1}(\%) \times \frac{W_{pass\ 1}}{Total\ W} + RBC_{pass\ 2}(\%) \times \frac{W_{pass\ 2}}{Total\ W} + \dots + RBC_{pass\ n}(\%) \times \frac{W_{pass\ n}}{Total\ W}$$

where $RBC_{pass\ i}$ is the individual pass with RBC measurement; and n is the total number of passes for each subject.

Other clot composition data (e.g., fibrin, white blood cells etc.) will be calculated in the same fashion as RBC, in terms of clot area and weight separately. All clot composition will be summarized across all subjects per pass and overall.

7.8 Analyses of Adverse Events (AEs)

AEs will be analyzed using safety analysis set. The number of events, the number and percentage of subjects with at least one event will be summarized by body system organ class and preferred term using the latest version of Medical Dictionary for Regulatory Activities (MedDRA), overall and by following categories.

- All AEs
- Serious adverse events (SAEs)
- Device and/or procedure related AEs
- Device related AEs
- Procedure related AEs
- Unanticipated serious adverse device effects (USADEs)

The independent clinical event committee will make adjudications for device and/or procedure related SAEs as specified in the PERFECT study Clinical Event Committee Charter.

7.9 Plans for Interim Analyses

Interim analyses will be conducted for regional (outside Europe, as well as for European MDR) regulatory submission purposes. Only descriptive statistics will be reported. Results of the interim analyses will not be used as a basis for stopping the trial early.

7.10 Handling of Missing Data

Missing data for the primary analysis of mRS ≤ 2 at 90 days (section 7.5.2.1) will not be imputed. The imputation of missing mRS scores at 90 days for sensitivity analysis is detailed in section 7.11.

There are no other missing data imputation planned in the study.

7.11 Sensitivity Analyses

- mRS ≤ 2 at 90 days

mRS sensitivity analyses will be based on mITT analysis set.

Due to reasons other than all-cause mortality, missing mRS scores at 90 days (75 days or above) will be imputed using the last non-missing post-procedure mRS score (e.g., mRS score from discharge or any unscheduled visits) if available. Subjects without any post-procedure mRS scores will be excluded from sensitivity analysis.

The mRS ≤ 2 at 90 days will also be analyzed by the window of ± 15 days using observed data (without last observation carry forward imputation).

7.12 Subgroup Analysis

- The primary endpoint will be analyzed by subgroups with clinically meaningful risk factors using the mITT analysis set. Additional subgroup analyses may be performed as applicable. Descriptive statistics for each subgroup will be presented when there is a minimum of 10 subjects in all subgroup levels, CIs will not be provided due to limited sample size.
 - Age at consent (years)
 - Vascular location
 - ASPECTS score
 - Baseline NIHSS
 - Aspiration device position when aspiration started in pass 1
- The following bullets will be analyzed for primary endpoint, secondary effectiveness and safety endpoints, demographic and baseline characteristics using the analysis set (as defined from section 7.3 to section 7.5). Descriptive statistics will be

presented based on observed data; CIs will not be presented due to limited sample size.

- System approach of EMBOVAC in combination with Cerebase (long sheath)

Descriptive statistics will be presented if the number of subjects who have used CEREBASE at least once during the procedure is greater than 10 , by following category:

EmboVAC + any LS (including Cerebase)

EmboVAC + Cerebase only (no other LS other than Cerebase).

- Clots

Descriptive statistics will be presented by following category: tough clots vs. other clots.

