## PROTOCOL SUMMARY

Title of Study	Prospective Evaluation to Characterize the Real-World Performance of the EMBOVAC™ Aspiration Catheter for Neurothrombectomy: A Post-Market Clinical Follow-up Trial.	
Short Title	PERFECT	
Study Sponsor	CERENOVUS [name]	
Study Device	EMBOVAC™ Aspiration Catheter	
Indication	The EMBOVAC™ Aspiration Catheter is indicated for general intravascular use in the neuro vasculature. The catheter can be used to facilitate introduction of diagnostic or therapeutic agents and is also intended for use in removal/aspiration of emboli and thrombi from selected blood vessels in the neuro vasculature.	
Study Design	Prospective, multi-center, single arm, post-market clinical follow-up study.	
Sample Size	Approximately 100 subjects will be enrolled.	
Number of Sites	Approximately 10 institutions primarily in Europe.	
Study Duration	Start Date: 2020	End Date: 2022
Study Procedures	
EMBOVAC™ Aspiration Catheter is used with ADAPT (A Direct Aspiration, First Pass Technique) as the first attempted device/technique for mechanical thrombectomy in the subject.
 
The study evaluation time points follow the site's standard of care and include:
 
 
1. Study Procedure
 
2. 24 Hour follow-up (+/- 12 hrs)
 
3. 7 Day / Discharge follow-up (-1/+7 days) (whichever comes first)
 
4. 90 Day Follow-up (+/- 14 days)
 
	
Primary Objective	The primary objective of this Post-Market Clinical Follow-Up (PMCF) study is to characterize the performance of the EMBOVAC™ Aspiration Catheter in the treatment of acute ischemic stroke in a real-world clinical setting.	

Secondary Objective	The secondary objective is to confirm the benefit of a 'system approach' using Cerenovus products (e.g., distal access catheter, balloon guide catheter) which have been designed for use together in the treatment of acute ischemic stroke.
Primary Endpoint	Proportion of patients having successful revascularization, defined as number of subjects achieving a modified Thrombolysis in Cerebral Infarction (mTICI) score of $\geq 2b$ at the end of the procedure, as determined by Core Lab.

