### 1.3.1. Rationale

This study aims to assess the performance of the EMBOVAC™ Aspiration Catheter when used by multiple interventionalists and centers in a real-world clinical setting, as well as to explore the benefit of a ‘system approach’ using the Cerenovus products which have been designed for use together in the treatment of acute ischemic stroke (e.g., distal access catheter, balloon guide catheter). This study will also look at association between clot composition and reperfusion in order to gain better insight into the etiology of the disease and means for effective clot removal.

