## **2. Objectives and Purpose**

### **2.1. Objectives**

The primary objective of this post-market clinical follow-up (PMCF) study is to characterize the performance of the EMBOVAC™ Aspiration Catheter in the treatment of acute ischemic stroke in a real-world clinical setting, as well as to confirm the benefits of a “system approach” using the Cerenovus products which have been designed for the use together in the treatment of acute ischemic stroke (e.g., distal access catheter, balloon guide catheter).

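### The only analysis of the system approach sets all long-sheath users beside their own Cerebase-only subset, so no displayed group was treated without Cerebase

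*SAP*

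**What the plan says.** **Objective.** The Protocol Summary states: "The secondary objective is to confirm the benefit of a" system approach. It describes the parts of that system as "Cerenovus products (e.g., distal access catheter, balloon guide catheter) which have been designed for use together". Protocol 2.1 places the same aim inside the primary objective: "as well as to confirm the benefits of a" system approach. Protocol 1.3.1 is weaker: "as well as to explore the benefit of a" system approach.

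**Analysis.** Protocol section 10 contains no analysis for this aim. SAP 7.12 contains one, under "System approach of EMBOVAC in combination with Cerebase (long sheath"). It covers the primary endpoint, the secondary effectiveness and safety endpoints, and demographic and baseline characteristics. It is descriptive and has no confidence intervals. It is produced only if "the number of subjects who have used CEREBASE at least once during the procedure is greater than 10". The two categories are:

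- "EmboVAC + any LS (including Cerebase")
- "EmboVAC + Cerebase only (no other LS other than Cerebase")

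The rest of SAP 7.12 is built differently. The clot analysis sets tough clots against other clots, which are separate groups. The risk-factor subgroups require at least 10 subjects in every level shown.

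**The concern.** A claim that adding Cerebase helps needs patients with Cerebase beside patients without it. The plan shows long-sheath users beside a subset of themselves. If the SAP is followed exactly, the table has no comparator free of Cerebase. A reader who sets the two columns against each other sees a reduced gap and cannot tell how far it was reduced by patients who used both kinds of sheath.

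Two further matters follow. The threshold does not control the size of the column that carries the Cerebase result. And the balloon guide catheter, one of the objective's own examples, has no specified category. What is at stake is whether the system-approach objective can be addressed as the protocol words it. The primary endpoint analysis is not touched.

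**Working it through.** **1. The plan's only precision figure.** SAP section 6 gives a margin of 8.0% for the primary endpoint. Check: 1.96 × √(0.8 × 0.2 / 95) = 8.04%, so it reproduces. It concerns the whole cohort; no precision is stated for the system approach.

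**2. Who is in each column.** Patients fall into four groups: (A) Cerebase as the only long sheath, (B) Cerebase plus another long sheath, (C) another long sheath only, (D) no long sheath. The first category is A + B + C and the second is A. Only C and D were treated without Cerebase, and neither is displayed.

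**3. Shrinkage.** Let f = n(A) / n(A+B+C), let p_A be the rate in A and p_R the rate in B and C together. Then

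any-sheath rate = f·p_A + (1 − f)·p_R, so p_A − any-sheath rate = (1 − f)(p_A − p_R).

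This is exact for observed proportions. The documents give no sheath counts, so f is an assumption:

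| f | a 10-point gap (A against B + C) is displayed as |
|---|---|
| 25% | 7.5 points |
| 50% | 5 points |
| 80% | 2 points |

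**4. Can the missing group be recovered by subtraction?** Suppose the columns read 16/20 (80%) and 37/50 (74%). Here f = 20/50 = 0.40 and the remainder is 21/30 (70%), so the displayed gap is 6 = 0.6 × 10 points. The same display fits two different situations:

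- Nobody used both: C = 21/30 (70%), and A − C = 10 points.
- Some used both: B = 5/10 and C = 16/20 (80%), and A − C = 0 points.

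The SAP's qualifier about no other sheath allows for group B, and the two columns do not show its size. Group D can be obtained for a binary endpoint from the whole-cohort table: with an assumed 76/95 overall, 76 − 37 = 39 of 95 − 50 = 45. That does not work for medians, or for the Kaplan-Meier rates that SAP 7.5.2.2 uses for device-related serious adverse events and mortality.

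**5. The threshold.** Eleven patients with any Cerebase use satisfy it. If, as an assumption, only 5 of them used no other long sheath, the Cerebase-only column has 5 patients. A result of 4/5 has an exact 95% interval of 28.4% to 99.5%, which the SAP would not display.

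**6. What separate groups could show.** With 80% assumed in both groups, Newcombe 95% half-widths for a difference are:

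| Group sizes | Half-width (points) |
|---|---|
| 47 vs 48 | 16.1 |
| 30 vs 65 | 17.2 |
| 20 vs 75 | 19.4 |
| 11 vs 84 | 23.7 |
| 20 vs 20 | 24.7 |
| 11 vs 11 | 32.7 |

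The first four rows use all 95 evaluable patients, leaving the other sheath groups empty.

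**The case against.** **No contrast is planned.** The SAP displays statistics by category, plans no hypothesis tests, and writes an explicit versus only for clots. The Cerebase-only column still reports every listed endpoint for EMBOVAC with Cerebase. This stands as far as it goes: the plan makes no false inferential claim. It does not rescue the objective, because a benefit cannot be described without a group that lacks the component.

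**Other tables may fill the gap.** Protocol 7.3 collects devices used per pass, SAP 7.4 summarises procedural characteristics, and SAP 7.12 allows additional subgroup analyses. Device counts could therefore appear somewhere. But the rows in SAP 7.4 are not specified, and the allowance in 7.12 sits under the risk-factor subgroups. Neither specifies the missing comparison.

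**The components are examples.** A reader might infer that the SAP ignores the components named in the objective. The documents do not support that. The list is introduced by e.g., so a long sheath may belong to the system, and the distal access catheter may be EMBOVAC itself; the documents do not say. Only the balloon guide catheter point remains, and it is secondary.

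**The numbers are constructed.** This is correct. The wording permits use of two sheath types but does not suggest that it is common.

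**Separate groups will not settle the matter.** Also correct. For 16/20 against 21/30 the Newcombe interval runs from about −15 to +31 points. That is a reason to change the objective's wording; it does not justify overlapping categories.

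**Conclusion.** The plan is wrong as written on this point. Followed exactly, the only specified system-approach analysis displays no group treated without Cerebase, reduces any visible contrast in proportions by the factor (1 − f), and sets a threshold that does not govern the Cerebase-only column. These conclusions rest on the text and on algebra, and need no assumed counts. How large the reduction will be, and whether the Cerebase-only column will be small, are unknown because sheath use is not given anywhere.

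A reader might go further and infer that the study's main result is compromised, or that better categories would let the study confirm a benefit. Neither is supported. The primary endpoint is analysed in the whole mITT set. Sheath choice is not randomised, no tests are planned, and a between-group difference would carry a half-width of roughly 16 to 33 points at the assumed sizes. The change should be made, but it concerns a descriptive analysis and the wording of one objective.

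**What to change.** **SAP 7.12.**

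- Replace the two categories with four mutually exclusive groups: Cerebase as the only long sheath; Cerebase plus another long sheath; other long sheath only; no long sheath.
- Always show the count in each group, and apply the greater-than-10 rule to each group whose outcomes are displayed.
- State that sheath choice was not randomised and that the display is descriptive.
- Either add a balloon guide catheter category, if the data are collected, or state that only the long sheath is examined.

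Confidence intervals and a between-group difference are optional. If intervals are added for small groups, use exact or Wilson intervals. The normal approximation gives 59% to 105% for 9/11.

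**Protocol Summary and Protocol 2.1.** Change *confirm* to *explore*, matching Protocol 1.3.1, and list the aim as a secondary objective in both places.

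**Cost.** The four groups follow from what the present threshold and categories already require: any long sheath, Cerebase at least once, Cerebase only. The sheath change therefore needs revised table shells and a few sentences of SAP text; optional intervals would add method text and programming. A balloon guide category depends on what the eCRF records, which the documents do not show. The protocol wording needs ethics committee review under Protocol 11.2, but the SAP change need not wait for it. The downside is that some groups may fall below the threshold, so that only their counts are shown.

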7.13 Additional Analyses

- Protocol deviations

The number of deviations, the number and percentages of subjects with any protocol deviation will be summarized overall and by deviation category.

- Device malfunctions/deficiency

Subjects with at least one device malfunctions/deficiency will be listed.

- NIH Stroke Scale (NIHSS) total score

The NIHSS total score and change from baseline will be summarized at the scheduled visits with observed data.

- mTICI scores

All mTICI scores will be summarized by pass and at the end of study procedure using the assessments from the core lab.

- mRS scores

mRS scores by categories of 0, 1, 2, ..., 6 will be summarized at scheduled visits using mITT analysis set. A shift table of mRS score from baseline to 90-day follow-up will be summarized as well.

7.14 Changes from Planned Analyses

- Analysis window mRS \leq 2 at 90-day

Due to the potential impact of Covid-19, it is expected that there may be more late 90-day mRS assessments compared to the SAP-defined 90-day window of ± 15 than

anticipated. In order to minimize the impact of out of 90-day window assessments, analyses on mRS endpoint will include all available assessments on or after 75 days. Analyses using the 90-day window of ± 15 days will be considered part of the sensitivity analyses (section 7.11).

Other study endpoints at 90 days (e.g., all-cause mortality at 90 days, device and/or procedure related SAEs at 90 days) will still be based on the 90-day window of ± 15 days considering the event days are not restricted by the compliance of the 90-day visit.

End of Document
